Title: A randomised crossover trial of five cryocompression devices' ability to reduce skin temperature of the knee.

NCT Number: NCT05355116

Document Date: This version to be uploaded to ClinicalTrials.gov was created on 16th May 2024, though the content below is a carbon copy of the protocol that was approved by the institutional review board on 11th March 2022 prior to the beginning of the study.

Device comparison study protocol (approved by IRB on 11th March 2022)

Introduction

Cryotherapy after surgery is widely utilised and has numerous practical applications for post-operative rehabilitation. Previous research has suggested that during cold therapy, the skin temperature of the knee should be reduced to 10-15°C to maximise the therapeutic benefits of cooling while avoiding the risk of cold injuries such as nerve damage and frostbite (Wilke and Weiner, 2003; Bleakley, McDonough and MacAuley, 2004). However, a recent study noted that where cryocompression devices have previously been used to reduce the skin temperature <10°C, no complications relating to the device have been reported, suggesting that the risk to the user at these lower temperatures is minimal (Bellon *et al.*, 2019). The temperature range at which a cryocompression device should be set in order to achieve a skin temperature within the therapeutic range of 10-15°C is unknown. Furthermore, there is evidence to suggest that the temperature of the device does not equal that to which the skin is reduced (Selfe *et al.*, 2009). Therefore, it is not sufficient to assume that the temperature setting of a cryocompression device accurately reflects skin temperature. Modern cryotherapy devices often consist of some sort of cuff that can be wrapped around the knee, with a connecting tube to a central unit that supplies and circulates ice-water to and from the cuff in order to cool the intended body part. Such devices offer differing levels of control over the temperature of the ice-water as it leaves the central unit, but nothing is known about how this correlates to the skin temperatures that are achieved during a cryotherapy treatment.

The aim of this study is to determine the ability of five different cryocompression devices to effectively lower the skin temperature of the treatment area to within the therapeutic range.

Methods

Design

This prospective randomised controlled trial will recruit healthy adult volunteers from a university population to participate. To avoid the involvement of individuals with unequal relationships, participants will be recruited through the form of advertisements on staff and student noticeboards, and through an email invitation sent to students within the faculty. A power analysis demonstrated that a total of 30 participants would be required to achieve a power of 0.8 and alpha error probability of 0.05 for a small-medium effect size of $f=0.2$. Each participant will take part in every condition to eliminate the risk of demographic factors confounding the results. Each of the 5 devices being investigated will comprise each of the test conditions. The order in which participants complete the 5 test conditions will be randomised in advance using a computer random number generator. Testing will involve each device being applied and used according to the manufacturers' instructions. Where a device has the ability to apply different temperatures and pressures to participants, settings will be selected in accordance with manufacturer guidelines and recommendations for use. Each testing session will take around 60 minutes to complete, depending on the treatment application guidelines of each device, with at least 24 hours between tests involving the same participant. In total, participants will be giving around 5 hours of time across 5 days to complete their participation.

Inclusion and exclusion criteria

Participants ≥ 18 years old will be considered eligible for the study unless they meet any of the following exclusion criteria, which include the common contraindications for cold therapy (Selfe *et al.*, 2009; Fang *et al.*, 2012; Waterman *et al.*, 2012):

- BMI >40 kg/m²
- History of nerve damage or sensory deficit in the lower limbs (including frostbite)
- Hypersensitivity to cold, including hives
- Active inflammation or pain of the knee
- History of thrombosis, embolism, or other conditions related to impaired peripheral circulation
- Suffering from diagnosed diabetes, multiple sclerosis, rheumatoid arthritis, spinal cord injury, cardiovascular disease, hypertension, Raynaud disease, cryoglobulinemia, or haemoglobinuria
- Confirmed or suspected tissue infection, an unstable fracture, a skin condition, or a tumour in the treatment area
- Cognitive impairment or communication barriers where adjustments can not be reasonably made

Protocol

All eligible participants will first be required to provide informed consent prior to their participation in the study. Once this has been obtained, participants will each attend 5 individual testing sessions, each lasting no longer than 60 minutes. The height and mass of the participants will be measured during the first testing session in order to calculate BMI, and participants' age and sex will be recorded and included in the later data analysis.

Participants will be required to remain in a seated position with their leg in full extension and elevated, parallel to the floor, for the duration of each test. The leg that will be used for the study will be randomly selected for each participant, and will remain the same for each condition. Skin temperature will be measured using a thermocouple, which will be attached with tape 20 mm distal to the patella. One of the cryocompression devices (Physiolab S1; Physiolab ice pack; GameReady; Cryo/Cuff; or VPulse) will then be attached to the leg of the participant and the test will begin. Depending on the condition to which a participant has been randomly assigned for a given test, a different device will be used. The temperature and pressure settings for each test will be set according to the manufacturers' recommendations which vary between devices. The lowest temperature setting that will be used throughout the study will be 1°C (GameReady device) and the highest pressure setting that will be used is 50 mmHg (GameReady and Physiolab S1 devices). None of the temperature or pressure settings used are deemed to be unsafe or have a high risk of adverse reactions, as long as participants are not contraindicated according to the abovementioned exclusion criteria.

The temperature of the skin will be measured using a k-type thermocouple attached to an infrared thermometer immediately prior to the application of a device, and then every 5 minutes for the duration of the test. The length of a test will be 30 minutes, in accordance with the manufacturers' instructions/recommendations for each device.

Upon completion of a test, the cuff will be removed. If the temperature of the skin has been reduced to within 10-15°C, skin temperature will continue to be monitored every 5 minutes after the cuff has been removed until it rises above 15°C, at which point the test will end. This will allow for the total time to be measured that skin temperature remains within the target therapeutic range as a result of a single application of the cryocompression device. If the skin temperature is not reduced to within 10-15°C while the cuff is worn, then the test will end after the cuff is initially removed. Upon completion of the test, the temperature sensor will be removed from the leg of the participant; thus completing their participation in the test. Once each participant has taken part in all conditions, they will have completed their participation in the study.

The following measures will be recorded: skin temperature at each time point, minimum skin temperature achieved, time to achieve minimum skin temperature, length of time with skin temperature within therapeutic range of 10-15°C. After each test, participants will also be asked to respond to the following question using a 5-point Likert scale: "How comfortable did you find the treatment you just experienced?" The possible answers to this question will be: "Very comfortable, Comfortable, Neutral, Uncomfortable, Very uncomfortable". This will provide insight into differences in perception of the treatment, which could be relevant for the likelihood of protocol adherence by patients in clinical settings.

Analysis

The data will be analysed to detect any differences during testing compared to baseline measures, and between groups. All data will be first subjected to a Kolmogorov-Smirnov test to assess whether they are normally distributed. A repeated measures analysis of variance will be performed on all normally distributed data. A Friedman test will be performed on any data that are not normally distributed.

Ethical issues

There is a low risk of cold injury to participants if their skin temperature is reduced to <10°C for any prolonged period of time (>60 mins). The coldest temperature setting for this study is 1°C (GameReady), which will be applied for 30 mins. A recent study conducted at the University of Winchester demonstrated that device temperature settings do not equal the actual skin temperatures achieved, and it is not expected that skin temperatures will be reduced to lower than 6°C for more than 15 minutes during any test. Therefore, the risk of harm to the participant is deemed to be minimal for this study.

Participants have the right to withdraw themselves and any collected data from the study at any time during, and for the first 7 days after, their participation without having to give a reason. They also have the right to terminate a test session at any time. Testing shall also be terminated as a result of any adverse reactions that emerge. Adverse reactions (e.g. pain) to the testing protocol are not expected due to the low-risk nature of the study, however any that occur shall be recorded and monitored until things return to baseline/normal. In

order to monitor any pain/discomfort that might occur, a Numerical Pain Rating Scale (0-10 scale) will be within sight of the participant at all times during testing: a test will be terminated if reported pain/discomfort exceeds 5/10, though none is expected. Any reported pain (or other adverse reactions) shall be stored along with the data collected for that participant. If a test is terminated for a reason that could be mitigated in future, participants will be offered the opportunity to repeat the test another day, should they wish to continue taking part in the study. If a test is terminated due to an adverse reaction that can not be mitigated in future, the participant (and any collected data) will be thanked for their time and withdrawn from the study.

Conflict of interest declaration

[name] (JB) receives payment from Physiolab Technologies Ltd as an external research consultant. Physiolab Technologies Ltd have had no influence on the design of the study. Although the study is being led by JB, who will proceed in his role impartially, the co-authors of this research will assist with the data collection, analysis, and eventual manuscript preparation to ensure that any unethical investigator biases are avoided. In addition to the consultancy fees for JB, Physiolab Technologies Ltd will provide the equipment to be used in this study. The other authors of this work have no conflict of interest to declare.

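### The repeated measures ANOVA for this five-session crossover has no session term, so any shift shared by participants across sessions would cost power; this concerns efficiency, not validity.

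*Combined protocol and SAP*

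**What the plan says.** Under Design, every participant uses all five devices, with sessions a day or more apart: "The order in which participants complete the 5 test conditions will be randomised in advance using a computer random number generator". The same section gives the sample size: 30 participants for power 0.8 at alpha 0.05 and f = 0.2.

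The Analysis section is short. Its aim is: "The data will be analysed to detect any differences during testing compared to baseline measures, and between groups". After a Kolmogorov-Smirnov check there are two routes: "A repeated measures analysis of variance will be performed on all normally distributed data", and "A Friedman test will be performed on any data that are not normally distributed". Neither names session, period or order.

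The only further variables said to enter the analysis are in the Protocol section: "age and sex will be recorded and included in the later data analysis". That section also says when skin temperature is read: "immediately prior to the application of a device, and then every 5 minutes for the duration of the test". The derived outcomes listed there are "minimum skin temperature achieved, time to achieve minimum skin temperature, length of time with skin temperature within therapeutic range", and a comfort rating is taken after each test.

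**The concern.** A participant's readings may shift from the first session to the fifth for reasons unrelated to the device, such as familiarity with the procedure, room conditions or rating habits. Because order is randomised, such a shift does not favour any device on average. It does add variation between one person's five results. An ANOVA with only participant and device counts that variation as error.

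Age and sex cannot remove it. Both are constant within a person, so as main effects they explain nothing that differs between that person's sessions. Session number could remove the shared part, and it is known for every test because the orders are generated in advance. The stake is power for the device comparison in a trial of 30 people.

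**Working it through.** **Inputs from the documents (Design):** N = 30, 5 devices, 5 sessions, f = 0.2, alpha 0.05, target power 0.8.

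**Assumptions, not in the documents:** within-person correlation rho = 0.5 (range 0.3 to 0.7), sphericity, one value per session, independent random orders, and a linear drift of d within-person SD per session shared by all participants.

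**1. The plan's own figure.** The noncentrality is lambda = N × 5 × f² / (1 − rho) = 30 × 5 × 0.04 / 0.5 = 12, on 4 and 116 df. Power is 0.784. Reaching 0.80 needs N = 32, or rho = 0.517 at N = 30. The stated 30 is reproduced to within two participants.

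**2. Without a session term.** The centred drift values are −2d, −d, 0, d and 2d. Their sum of squares is 10d², and 10d²/4 = 2.5d². Under independent random orders the expected error mean square grows by the factor 1 + 2.5d², so lambda = 12 / (1 + 2.5d²). At d = 0.25 this is 12 / 1.15625 = 10.38.

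**3. With a four-df session factor.** Independent random orders lose on average 1/30 of the device information, so lambda = 12 × 29/30 = 11.6, on 4 and 112 df. Power is 0.767 whatever the drift.

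**4. With a one-df linear term.** Only one of the four session contrasts is fitted, so the average loss is (1/30)/4 = 1/120. Then lambda = 12 × 119/120 = 11.9, on 4 and 115 df, and power is about 0.78 if the drift really is linear.

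| Drift d (SD per session) | No session term | Four-df factor | Equivalent N without session, 30/(1 + 2.5d²) |
|---|---|---|---|
| 0 | 0.784 | 0.767 | 30 |
| 0.13 | 0.765 | 0.767 | about 29 |
| 0.25 | 0.714 | 0.767 | about 26 |
| 0.5 | 0.546 | 0.767 | about 18 |

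Simulation with 20,000 trials per scenario agrees: 0.781, 0.763, 0.720 and 0.550 without session, against 0.767, 0.768, 0.773 and 0.771 with the factor.

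**5. Break-even.** The four-df factor equals the unadjusted test at d = 0.12, which is 4 × 0.12 = 0.48 SD from session 1 to session 5. The linear term breaks even at about 0.06.

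**6. Sensitivity to rho.** For d = 0, 0.13, 0.25 and 0.5, unadjusted power at rho 0.3 is 0.619, 0.598, 0.548 and 0.401, against 0.601 with the factor. At rho 0.7 it is 0.957, 0.948, 0.923 and 0.795, against 0.950. The four-df break-even stays at 0.12.

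**7. A different shape.** If only session 1 differs, by 1 SD, simulated power is 0.695 without session and 0.765 with the factor.

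**8. Type I error.** Under independent orders the simulated size of the unadjusted ANOVA was 0.048 to 0.052 over these drifts. If orders were balanced, the whole session sum of squares would fall into error while the device mean square was unaffected. F would then shrink by 1 + 30 × 10d²/116, which is 1.16 at d = 0.25. The size there is about 0.03, so the test is conservative.

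**The case against.** The strongest objection is that no drift is documented. Order is randomised, sessions are separated, and nothing in the text suggests a trend by session number. With no drift the factor lowers power from 0.784 to 0.767, slightly further below the planned 0.8. This stands, and it makes the benefit conditional.

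A second objection is that the pre-application reading already protects some outcomes. If temperature is analysed as change from that reading, a shift common to both readings cancels. This stands in part. The plan applies the baseline comparison to its data in general and does not say which outcomes are analysed as changes.

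Third, a common session factor removes only what participants share. Person-specific trends stay in error with or without it. This stands too.

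A reader might also infer that the Friedman test should be replaced, since in its standard form it has no place for session. The documents do not support going that far. The effect of replacing it depends on how comfort ratings and time in range are distributed, which the plan does not give. Under one assumed symmetric comfort pattern with no drift, a linear score model with session had power 0.686 against 0.661 for Friedman. Under a strongly skewed pattern the two were level (0.490 against 0.491). For time in range with about 60% zeros assumed, Friedman did better (0.497 against 0.478).

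**Conclusion.** The point holds as an efficiency point about the repeated measures ANOVA. The plan names no session term, and any shared session shift lowers the power of the device test. At rho 0.5 the four-df factor gains about 5 power points at a drift of 0.25 SD per session (0.767 − 0.714) and about 22 at 0.5 (0.767 − 0.546). It loses about 1.5 at zero drift. The 0.5 case is an upper illustration, not an expectation.

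Two stronger readings are tempting and should be resisted. A reader might infer that the missing term biases the device comparison or raises the false-positive rate. It does neither: size is about 0.05 under independent orders and below that under balanced ones. The plan says only that a random number generator is used, so either is possible. A reader might also take 0.12 as the drift at which loss begins. Any drift lowers unadjusted power; 0.12 is only where a four-df factor overtakes omission under independent orders. With balanced orders that crossing would come at about 0.02.

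The figures rest on assumed rho, sphericity, a drift shared by all participants and one value per session. That the term is missing is certain. How much adding it would gain is not known.

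**What to change.** In the Analysis section, pre-specify session number (1 to 5) as a fixed effect alongside device, with participant as a random or block effect, for the outcomes analysed by repeated measures ANOVA. State in advance whether session enters as a factor or as a linear term. The factor assumes no shape for the drift. The linear term is cheaper but relies on the drift being roughly linear.

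Keep the Friedman test as planned for non-normal outcomes and for comfort. A session-adjusted analysis of these may be added as a sensitivity analysis.

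The cost is four error df (116 to 112) and about 1.5 power points if there is no drift, or one df and about half a point for the linear term. The order list need not change, and no extra visits, participants or measurements are needed.

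### The plan states no balancing of device order over sessions and no session term; 30 participants fit a Williams design exactly, and it should be paired with a session-adjusted analysis

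*Combined protocol and SAP*

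**What the plan says.** Methods, Design, describes a complete five-device crossover: "Each participant will take part in every condition to eliminate the risk of demographic factors confounding the results". The only sentence on how orders are produced is "The order in which participants complete the 5 test conditions will be randomised in advance using a computer random number generator". No Latin square, Williams design, blocking or list of sequences is named there or elsewhere. Sessions are spaced "with at least 24 hours between tests involving the same participant".

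The same section gives the sample size: "a total of 30 participants would be required" to "achieve a power of 0.8 and alpha error probability of 0.05", for an effect size f of 0.2.

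The Analysis section plans a repeated measures analysis of variance for normally distributed data, and otherwise "A Friedman test will be performed on any data that are not normally distributed". It names no session (period), sequence or carry-over term.

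**The concern.** In a five-period crossover, anything that changes from session to session can be mistaken for a device difference if devices are spread unevenly over sessions. Examples are getting used to cold, staff becoming practised with the cuffs, or comfort being judged against the last device tried. As written, neither the design nor the analysis controls this. The order sentence guarantees no balance, and neither planned test removes a session effect. The comfort rating is the most exposed outcome: it is a 5-point scale, so it is likely to go to the Friedman test, which has no place for a session term.

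The sample size already suits a fully balanced order scheme, so the precision at stake could be had almost free.

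**Working it through.** **Inputs.** From the protocol: 30 participants, 5 devices, 5 sessions, alpha 0.05, power 0.8, f = 0.2. Assumed, because the documents do not give them: correlation 0.5 between a person's sessions, sphericity, and a linear drift of d within-person (residual) SD per session. The check treats each session as giving one value per outcome.

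**The plan's own figure.** For the within-subject F test, the noncentrality is f² × N × 5 / (1 − correlation) = 0.04 × 30 × 5 / 0.5 = 12, with 4 and 116 degrees of freedom. Power is 0.784 at N = 30, and N = 32 is needed to reach 0.80. So 30 is approximately reproduced at correlation 0.5. The result depends on that assumption: N would be 43 at 0.3 and 20 at 0.7.

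**Imbalance if orders are drawn freely.** In a random ordering of 1 to 5, a device's position has variance (25 − 1)/12 = 2, and two devices' positions have covariance −2/4 = −0.5. The difference has variance 2 + 2 − 2 × (−0.5) = 5. Over 30 people the SD of the difference in mean position is √(5/30) = 0.41 sessions. Simulating 20,000 order lists gave:

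- SD for a given pair of devices: 0.41 sessions, as derived.
- Largest gap in mean position between any two devices: median about 0.65, 95th percentile 1.1 sessions.
- Some device used 9 or more times in one session (6 if balanced): 98% of lists.
- Every device used exactly 6 times in every session: none of the lists.

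**Cost without a session term.** In residual SD units, a device difference has variance 2/30. Drift d adds d² × 5/30, so the relative increase is 2.5 × d²:

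| Assumed drift per session | Added variance | SD of a device difference |
|---|---|---|
| 0 | 0% | 0.258 |
| 0.1 | 2.5% | 0.261 |
| 0.2 | 10% | 0.271 |
| 0.3 | 22.5% | 0.286 |

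**Cost with a session term.** Free orders raise the variance of a device contrast by 3.7% on average (range 1.6% to 6.8% over the central 95% of lists) relative to balanced orders.

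**Does a balanced scheme fit?** A Williams design for five treatments has 10 sequences, and 3 × 10 = 30. Constructing it and counting gives every device 6 times in each session, and each of the 20 ordered device pairs 6 times in direct succession.

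**Is balance enough on its own?** Simulated type I error and power of the ANOVA at f = 0.2, correlation 0.5:

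| Drift | Orders | Session term | Type I error | Power |
|---|---|---|---|---|
| 0.3 | free | no | 4.7% | 0.69 |
| 0.3 | Williams | no | 2.1% | 0.67 |
| 0.3 | free | yes | 5.2% | 0.76 |
| 0.3 | Williams | yes | 5.4% | 0.79 |
| 0.5 | free | no | 4.9% | 0.55 |
| 0.5 | Williams | no | 0.5% | 0.44 |
| 0.5 | free | yes | 5.0% | 0.76 |
| 0.5 | Williams | yes | 5.2% | 0.79 |

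Balance takes the session shift out of the device means, but without a session term that shift stays in the error, so the test becomes conservative. The Friedman test behaves the same way: at drift 0.5 its power is about 0.30 with Williams orders against 0.41 to 0.43 with free orders.

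**The case against.** A reader might infer that the protocol specifies unrestricted orders. It does not. A random number generator can equally assign people to balanced sequences, so free ordering is an inference from silence. The imbalance and free-order cost figures are conditional on it.

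A reader might also infer that the imbalance biases the device comparison or invalidates the tests. It does not on average: random ordering makes devices exchangeable over sessions, and simulated type I error stays near 5% at every drift tried. A particular list can be unlucky. Among the tenth of lists with the largest position gap (at least 1.0 session), the ANOVA rejects a true null in 7.8% of trials at drift 0.2 and 10.8% at 0.3. That is a conditional rate, offset by other lists, and is a reason to prefer balance rather than evidence that the planned inference is invalid.

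The documents give no estimate of a session effect. The interval of at least 24 hours, the same leg throughout, and a standard posture and sensor site all make a large one less likely. A drift of 0.5 SD per session would add 62.5% to the variance, but it means a shift of 4 × 0.5 = 2 SD from first to last session, so it is an extreme case. With no drift, free ordering costs the planned unadjusted analysis nothing on average.

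Finally, balanced orders alone do not repair the plan, as the working shows, and withdrawals would make the balance only approximate. All of these points stand. They limit the size of the concern and shape the remedy. They do not remove the omission, or the fact that an exact scheme is available at this sample size.

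**Conclusion.** The point holds as one of precision and reporting. The protocol does not say whether device order is balanced, and no session term is planned. Under free ordering, marked imbalance is practically certain, at a cost of about 4% of contrast variance with session modelled, or 2.5% to 22% without it for drifts of 0.1 to 0.3 SD per session.

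In power terms, with session modelled, Williams orders give about 0.79 against about 0.76 for free orders. The session term itself matters more when drift is present: at 0.3 it moves power under free orders from 0.69 to 0.76. These figures assume correlation 0.5, sphericity, linear drift common to all participants, and no withdrawals. The change is worth making because it is cheap, not because the planned comparison is biased.

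**What to change.** Make both changes together.

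1. **Methods, Design.** Replace the order sentence with: *Participants will be allocated at random by computer, three per sequence, to the 10 sequences of a Williams design for five treatments, so that each device occurs six times in each session and directly follows each other device six times.* If balanced sequences were already intended, this sentence simply says so. State also whether a participant who withdraws is replaced on the same sequence.

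2. **Analysis.** Add: *Session (1 to 5) will be included as a factor in the repeated measures or mixed model.* For outcomes that would go to the Friedman test, such as the comfort rating, specify a session-adjusted analysis instead. Examples are an ordinal mixed model, or a mixed model on ranks, with device and session as factors.

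If the sessions have already been run, the first change is no longer possible. The report should then state how the order list was generated, and the second change still applies.

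Cost: a different order list, two or three sentences, and 4 degrees of freedom for session (error 116 to 112). There are no additional participants, visits or measurements. Balance becomes approximate after withdrawals; the session term then handles the remaining unevenness.

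### The 60-minute session maximum conflicts with the open-ended rewarming follow-up and, if enforced, could cut time in range short, coldest skin first

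*Combined protocol and SAP*

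**What the plan says.** Three statements in the combined protocol and SAP bear on how long a session may last.

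- **Protocol section, a maximum:** "participants will each attend 5 individual testing sessions, each lasting no longer than 60 minutes".
- **Design section, an estimate:** "Each testing session will take around 60 minutes to complete, depending on the treatment application guidelines of each device". The same paragraph adds that "participants will be giving around 5 hours of time across 5 days to complete their participation".
- **Protocol section, a stopping rule based on temperature alone:** once the cuff is off and the target range has been reached, "skin temperature will continue to be monitored every 5 minutes after the cuff has been removed until it rises above 15°C". That reading ends the test.

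The cuff-on period is fixed: "The length of a test will be 30 minutes, in accordance with the manufacturers' instructions/recommendations for each device". The reason given for the follow-up is this: "This will allow for the total time to be measured that skin temperature remains within the target therapeutic range". The resulting outcome is one of four listed temperature measures: "length of time with skin temperature within therapeutic range of 10-15°C".

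The Analysis section plans a repeated measures ANOVA, or a Friedman test where data are not normal. It has no provision for a duration still running when observation stops.

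**The concern.** A fixed maximum and an uncapped follow-up cannot both be guaranteed. When rewarming is slow, staff must either overrun the stated maximum or stop reading while skin is still at or below 15°C. The plan does not say which to do, nor how the second case is recorded.

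The consequence would not be even across devices. If rewarming follows the same rising curve whichever device was used, colder skin at cuff removal takes longer to pass 15°C. An enforced maximum would therefore reach the strongest coolers first and could only shorten their recorded time. The crossover design does not cancel this, because the cut depends on the device rather than the participant. Both planned tests would take the shortened value as a finished measurement. Without a written rule, overruns might also be handled differently from one session to another.

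**Working it through.** **Step 1: the plan's own figure.** 5 sessions × 60 min = 300 min = 5 h, which matches the Design section's total. Both figures are qualified as approximate there. The strict maximum appears only in the Protocol section.

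**Step 2: time left after cuff removal.** Allowance = 60 − 30 − s, where s is the time for sensor taping, device fitting, the baseline reading, the comfort question and, at the first session, height and mass. The documents give no value for s, so 0 to 15 min is assumed.

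| s (min) | Allowance (min) | Five-minute readings that fit |
|---|---|---|
| 0 | 30 | 6 |
| 5 | 25 | 5 |
| 10 | 20 | 4 |
| 15 | 15 | 3 |

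**Step 3: time needed.** The documents give no rewarming data. Assume exponential rewarming toward 31°C with time constant τ = 20, 40 or 60 min, from a skin temperature T0 at cuff removal.

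- Time to 15°C = τ·ln((31 − T0)/16).
- Time to re-enter the range at 10°C (for T0 below 10°C) = τ·ln((31 − T0)/21).

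Take T0 = 6°C. The Ethical issues section treats this as near the cold end of what is expected. Then ln(25/16) = 0.446 and ln(25/21) = 0.174.

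| τ (min) | Reaches 10°C (min) | Passes 15°C (min) | In range after cuff (min) | First scheduled reading above 15°C (min) |
|---|---|---|---|---|
| 20 | 3.5 | 8.9 | 5.4 | 10 |
| 40 | 7.0 | 17.9 | 10.9 | 20 |
| 60 | 10.5 | 26.8 | 16.3 | 30 |

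**Step 4: compare need with allowance.** From 6°C, the time to 15°C exceeds the allowance only when τ is above allowance/0.446. That is 67 min for an allowance of 30, 56 for 25, 45 for 20 and 34 for 15.

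- τ = 20: nothing is lost at any allowance.
- τ = 40: nothing is lost at 20 min or more. At 15 min, 17.9 − 15 = 2.9 min is lost.
- τ = 60: nothing is lost at 30 min. At 25, 20 and 15 min, the loss is 1.8, 6.8 and 11.8 min.

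The τ = 60 losses are 11%, 42% and 72% of the 16.3 min rewarming segment. The listed outcome also counts in-range time while the skin is cooling. If that is 5 to 10 min (assumed), the denominator is 21.3 to 26.3 min and the losses fall to about 7-8%, 26-32% and 45-55%.

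**Step 5: sensitivity to the rewarming target.** With targets of 22 to 30°C and τ of 20 to 60 min, time from 6°C to 15°C runs from 9 to 50 min. One case is a 22°C target with τ = 45, counting post-cuff time in range only:

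| T0 (°C) | True (min) | Recorded, 30-min allowance | Recorded, 20-min allowance |
|---|---|---|---|
| 6 | 24.3 | 17.1 | 7.1 |
| 8 | 24.3 | 23.1 | 13.1 |
| 10 | 24.3 | 24.3 | 20.0 |
| 12 | 16.1 | 16.1 | 16.1 |

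Here, even a session with no set-up time is cut from 6°C. At the 20-minute allowance, the device ending at 6°C records less than the one ending at 12°C, although its true time is longer. With τ = 20 and the same target, nothing is cut at either allowance.

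**The case against.** The strongest reply is that there is no hard limit in practice. The maximum rests on one clause, and the Design section's figures read as estimates of participant burden. The only operative rule for ending follow-up is the 15°C reading. The Ethical issues section lists reasons for ending a test early, and elapsed time is not among them. Nowhere does the plan say that readings stop at 60 minutes. The text fits investigators who simply expected rewarming to finish within the hour. **This stands.** It makes the concern conditional, but it does not say which statement governs when the hour runs out.

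A reader might go further and infer that the trial's time-in-range results are biased against the strongest coolers. The documents do not support that. They give no rewarming rate, no set-up time and no statement that the maximum was applied. Under moderate assumptions nothing is lost, and the large losses need slow rewarming, usually combined with a longer set-up.

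A reader might also infer that the measure most central to the study is at risk. That is contestable. The stated aim concerns bringing skin into the range, which the readings during application address, and a cut after cuff removal does not touch those readings. No measure is named as primary.

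Finally, standard right-censored analysis would not be a clean remedy. The cut is at a fixed session time, whereas the duration starts when skin enters the range. Slow rewarmers re-enter later and stay longer: with a 20-minute allowance from 6°C, τ = 60 leaves 20 − 10.5 = 9.5 min to observe a 16.3 min stay, while τ = 40 leaves 13.0 min for a 10.9 min stay. Censoring would then be related to the outcome. **This also stands**, and the fix takes account of it.

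**Conclusion.** The inconsistency is in the current text and should be removed. **If** the Protocol section's maximum were enforced, recorded time at 10-15°C could be too short, first for tests ending with the coldest skin. The direction rests on one assumption, a common rising rewarming curve across devices.

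The size cannot be fixed from the documents. It runs from nothing, if skin passes 15°C within the 15 to 30 minutes available, to a material loss if rewarming is slow. With a 31°C target and time constants of 20 to 60 min, 6°C skin needs 9 to 27 min. All these figures are illustrations under stated assumptions and do not predict what happens in this trial. The sample size and the temperature readings during application are not affected.

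**What to change.** 1. Reconcile the Design and Protocol sections so that 60 minutes is an **expected** session duration and does not end the post-cuff readings, which continue at five-minute intervals until one exceeds 15°C. Leave the participant's right to stop and the safety terminations as they are.
2. Record the time and skin temperature at the last reading of every test. Flag any test that ends with skin at or below 15°C as an incomplete duration, meaning that the true value is at least the recorded one.
3. State in the Analysis section that a flagged value is not analysed as complete without a sensitivity analysis showing whether the device comparison depends on how it is handled. Do not rely on standard right-censored methods alone, because the cut need not be independent of the duration.

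The cost is a minor amendment to the protocol and participant information, with ethics review because a stated maximum duration changes. Some sessions may run a few minutes longer. No extra participants or equipment are needed. If no session would overrun, the only cost is the amendment.
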